**Reporting Process**

The principal investigator or designee will complete and submit a FDA Form 3500A MedWatch for any event that meets the above criteria. Forms will be submitted to the CRS Compliance Office via email to [[contact]](mailto:[contact]). Network Sites refer to **Appendix A**.

**11 DATA AND SAFETY MONITORING**

Phase 1 studies will be reviewed at the scheduled RPCI Phase 1 meetings and the minutes are forwarded to the IRB for review. Phase I meets on a regular basis per the RPCI Data Safety Monitoring Plan.

The RPCI Data and Safety Monitoring Board will assess the progress of the study, the safety data, and critical efficacy endpoints. The DSMB will review the study annually and will make recommendations that include but not limited to; (a) continuation of the study, (b) modifications to the design (c) or termination of the study. Per request, all annual DSMB study outcomes will be made available to NCCN and BI.

**12 STATISTICAL METHODOLOGY**

This is a Phase I/II study. The Phase 1 is included to compensate for the current lack of toxicity information about nintedanib and capecitabine combination treatment. A standard 3+3 dose escalation design is considered, where a maximum of 18 patients are enrolled.

Phase II is a single arm – single stage study, where a total of n=36 (including 6 treated at the RP2D in Phase I) patients with refractory metastatic colorectal cancer will be enrolled and treated with a combination of nintedanib and capecitabine, as previously outlined. There is no formal interim analysis planned or early stopping rules. However, toxicity and safety outcomes will be regularly reviewed.

### **Endpoints**

- **Phase I**
  - Primary: Establishment of the recommended phase II dose.
- **Phase II**
  - Primary: The primary endpoint is the progression free survival (PFS) at 18 weeks. This will be assessed via the Response Evaluation Criteria in Solid Tumors (RECIST) version 1.1 guidelines after every 3 cycles (9 weeks) of therapy.
  - Secondary: Median progression free survival will be established. Median overall survival from the date of enrollment to the time of death will be documented. Aggregate rates of adverse events as measured by CTCAE v 4.0 will be recorded to objectively measure toxicities of the two agents.

The primary objectives of this study are:

- Phase I: To estimate the maximum tolerated dose (MTD) and examine the dose-limiting toxicities of nintedanib when administered with capecitabine within the study population and, establish the Recommended Phase II Dose (RP2D).
- Phase II: To assess progression free survival at 18 weeks. This will be assessed via the Response Evaluation Criteria in Solid Tumors (RECIST) version 1.1 guidelines after every 3 cycles (9 weeks) of therapy.

### **12.1 Sample Size Determination**

A maximum of 48 participants, 18 in Phase I and up to 30 additional patients for Phase II will be enrolled in this study. The number of participants required is a function of the unknown dose-limiting toxicity relationship and 18-week PFS rate. Accrual is expected to take 2 years.

#### **Sample Size Justification:**

In Phase I, using the standard 3+3 design, there will be a minimum of 9 and maximum of 18 patients enrolled.

In Phase II, the sample size calculations are based on the primary analysis of the 18-week PFS rate. Historically, the 18-week PFS rate is 5% and 25% for refractory metastatic colorectal cancer patients treated with placebo and regorafenib, respectively. The combination of nintedanib and capecitabine is expected to provide an 18-week PFS of at least 40% in patients with refractory metastatic colorectal cancer. The sample size calculation is based on testing hypotheses concerning the proportion of the treated population alive and progression free 18 weeks after enrollment. Let p represent the proportion of patients surviving with no evidence

of disease progression by RECIST at 18 weeks after start of treatment. A true PFS rate of less than  $p_0 = 0.25$  is considered unacceptable and evidence of such will deem the treatment not worthy of further study, as regorafenib has historically achieved this success rate. The null and alternative hypotheses to be tested are  $H_0: p = p_0$  versus  $H_1: p > p_0$ .

This single-stage design requires a total of 36 evaluable patients to achieve approximately  $1 - \beta$  power to detect a difference of at least  $\Delta$  percentage points ( $p_0$  versus  $p_0 + \Delta$ ). For calculations in this study,  $p_0 = 0.25$ ,  $\alpha = 0.10$ ,  $1 - \beta = 0.80$  and  $\Delta = 0.17$ . With these design parameters, the sample size was calculated using PASS v11.

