| Statistical Analysis | 
Sample Size Determination: Sample size determination for the phase I portion will depend upon the dose-toxicity profile, but is expected to be between 9-18 patients. For the phase II portion, with an alpha of 0.1, assessment of 36 patients allows for a power of 0.8 to detect a minimum difference of 17% in the PFS at 18 weeks, assuming a rate of 25% under standard of care.
 
Randomization: No randomization is required.
 
Efficacy Analysis: Primary interest is in the PFS at 18 weeks after enrollment. The PFS at 18 weeks will be described by binomial proportion estimates and 90% confidence intervals. All patients in the phase II study and those treated at the RP2D in the phase I study will be included for analysis.
 
Safety Analysis: Adverse events will be tabulated. AE rates will be described using binomial proportions and 90% confidence intervals.
 
Correlative Data Analysis: Mechanistic PK/PD modeling will be employed, examining the relationship between nintedanib pharmacokinetics, modulation of CAFs and PFS.
 |
|-----------------------------|--|

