#### 4.2 Target Accrual and Study Duration

It is expected that a total of 9 patients will be enrolled at two dose levels in the Phase I portion, with potential for a maximum of 18 patients. The number of participants required is a function of the unknown dose-toxicity relationship. Patients treated at the RP2D (n=6) will be included in the Phase II study analysis. Up to an additional 30 patients will be enrolled in the Phase II portion of the study, for a Phase II sample size of 36. Summarily, the study is expected to accrue 39 patients (9 + 36 - 6). However, if toxicity is greater than expected, a maximum of 48 patients might be required (18 + 36 - 6). Enrollment is expected to be split between the two sites involved: Roswell Park Cancer Institute and City of Hope. Thus, in the case of 39 patients being enrolled, it is anticipated that approximately 20 patients would be enrolled at RPCI and 19 at City of Hope. Accrual is expected to take up to 2 years. Median PFS has historically stood at approximately 2 months and this study aims to provide a PFS rate at 18 weeks (~4 months) of 40%. It is anticipated that patients will be on study for approximately 18 weeks.

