### *Primary Analysis:*

The Phase I portion of the study begins by enrolling 3 patients at Dose Level 1 (see **Table 2**). Standard 3+3 rules will be followed until the maximum tolerated (or administered) dose is found. The recommended Phase 2 dose will be considered tolerable if DLT(s) are observed in at most 1 of 6 patients completing at least 2 treatment cycles at that dose level. Available toxicity information about these drugs suggests that Dose Level 2 will be the recommended Phase 2 dose, and that 9 patients will be required for the Phase 1. The 6 Phase 1 patients treated at the recommended Phase 2 dose will be included in Stage 1 of the Phase 2 study.

The Phase 2 study's primary endpoint is the PFS rate, defined as the proportion of patients who survive without disease progression (per RECIST criteria) for least 18-weeks after the start of treatment. Patients who progress or die (due to disease or any cause) prior to 18-weeks will be counted as failures.

The following hypothesis about the true 18-week PFS rate ( $p$ ) will be evaluated using a one-sided exact binomial test:

$$H_0: p = 0.25 \text{ versus } H_1: p > 0.25.$$

If  $T = 12$  or fewer PFS responses are observed among the total  $n_1 + n_2 = 36$  evaluable patients, the therapy will be deemed ineffective; otherwise, it will be concluded that the therapy is promising. The analysis will be conducted in SAS v9.4 (Cary, NC) at a nominal significance level of  $\alpha=0.10$ .

*Secondary Analysis:* In Phase II the secondary outcomes include: overall (OS) and progression free (PFS) survival, and toxicities. A survival event is defined as a patient who experiences death from cancer or any cause, while a patient is considered censored if they are alive at the end of the

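### Is the 0.80 power misstated because the protocol names a 40% 18-week PFS rate but calculates power at 42%?

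*Combined protocol and SAP*

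**What the plan says.** The synopsis states that "assessment of 36 patients allows for a power of 0.8 to detect a minimum difference of 17% in the PFS at 18 weeks". The null rate behind that difference is the 25% which the synopsis takes for standard of care. Section 12.1 gives the same design in symbols: null rate 0.25, alpha 0.10, power 0.80, difference 0.17. It adds: "This single-stage design requires a total of 36 evaluable patients to achieve approximately" that power. Neither place writes out the resulting alternative of 42%.

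Two other statements give an efficacy expectation. Earlier in the same justification, 12.1 says "The combination of nintedanib and capecitabine is expected to provide an 18-week PFS of at least 40" per cent. Section 4.2, on accrual and duration, says "this study aims to provide a PFS rate at 18 weeks (~4 months) of 40" per cent.

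The primary analysis in 12.3 is a one-sided exact binomial test with a fixed rule. With 12 or fewer successes among the 36 "evaluable patients, the therapy will be deemed ineffective; otherwise, it will be concluded that the therapy is promising".

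**The concern.** In 12.1 the 40% expectation comes shortly before the hypotheses and the 0.80 power, so a reader may take the power to apply at 40%. The gap between 25% and 40% is 15 points, whereas the calculation uses 17, and no reason is given for the extra two. Section 4.2 names 40% without any qualifier.

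What would be at stake is the false-negative risk of the go/no-go rule. If the combination achieves exactly the rate in 4.2, the chance of declaring it ineffective is higher than the 20% that a reader would infer from a power of 0.80. The documents do not give the risk at that rate.

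**Working it through.** **Inputs.** Null rate 0.25, alpha 0.10, difference 0.17, n = 36 evaluable (synopsis and 12.1). One-sided exact binomial test, ineffective if 12 or fewer successes (12.3). Named rates: 40% (4.2) and at least 40% (12.1).

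**Step 1: the alternative used for power.** 0.25 + 0.17 = 0.42.

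**Step 2: the cut-off.** For a cut-off c, the attained alpha is P(X ≥ c) with X ~ Binomial(36, 0.25), that is, the sum over k = c to 36 of C(36, k) × 0.25^k × 0.75^(36 − k).

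- c = 12: 0.1671, above 0.10.
- c = 13: 0.0922, within 0.10.

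The smallest admissible cut-off is therefore 13, which is the rule in 12.3.

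**Step 3: the plan's own power.** P(X ≥ 13) with p = 0.42 is 0.8112. The stated 0.80 is reproduced. Moreover, 36 is the smallest n with exact alpha at most 0.10 and power at least 0.80 at 42%, so the sample size, test and cut-off all fit the stated difference.

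**Step 4: the same rule at other true rates.**

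| True 18-week PFS rate | P(13 or more of 36) | P(12 or fewer of 36) |
|---|---|---|
| 0.40 | 0.7385 | 0.2615 |
| 0.41 | 0.7766 | 0.2234 |
| 0.42 | 0.8112 | 0.1888 |
| 0.43 | 0.8421 | 0.1579 |

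Moving from 42% to 40% costs 0.8112 − 0.7385 = 0.0727 of power. Against the nominal 0.80, the shortfall at 40% is 0.80 − 0.7385 = 0.0615. Solving for power of exactly 0.80 gives a true rate of 41.7%.

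**Step 5: what designing for 40% would take.** The smallest n with exact alpha at most 0.10 and power at least 0.80 at 40% is 46 (16 or more successes; alpha 0.0896, power 0.8078). That is 46 − 36 = 10 more evaluable patients.

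**Step 6: does any statement conflict with another?** The synopsis and 12.1 both tie 0.80 to a 17-point difference from 25%, and they agree with each other. The expectation in 12.1 is a lower bound, which 42% satisfies. The figure in 4.2 comes with no alpha, power or difference, and it sits beside a median PFS of about 2 months and a conversion of 18 weeks to roughly 4 months. No document attaches 0.80 to 40%.

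**The case for a change.** The strongest case is that the power of a go/no-go design should be known at the rate the sponsors hope to see, and 4.2 states that rate without qualification. The word approximately in 12.1 covers 0.811 against 0.80 at 42%; it does not cover 0.738 at 40%. Even as a floor, 40% is the bottom of the expected range, and power there is below 0.80. A reader weighing a negative result would want to know that the rule misses a true 40% about 26% of the time.

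Part of this stands. The choice of 17 points over 15 is not explained, 4.2 is worded more loosely than 12.1, and power at 40% is not printed.

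It does not follow that the plan is wrong or incomplete where it matters. The null rate, difference, alpha, sample size, test and cut-off are all given, so power at any rate can be computed directly. A negative result will also not be read from the rule alone, because the synopsis commits to reporting the proportion with a 90% confidence interval. At the boundary of 12 of 36 (33.3%), the probability of 12 or fewer at a true 40% is 0.2615. That is well above 0.05, so an exact (Clopper-Pearson) 90% interval would still include 40%, and the report would show that 40% had not been ruled out. The plan does not name the interval method, so the exact one is an assumption here.

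**Conclusion.** The concern does not call for a change. The stated power is correct for the stated difference (exact 0.811 at 42%, alpha 0.092). The expectation in 12.1 is compatible with 42%, and the plain 40% in 4.2 is a narrative aim two points below the design alternative. At 40% the power is 0.738, about six points under the nominal 0.80, and the chance of a false negative is 0.262. Adding that figure would alter neither the sample size, the alpha, the 12-or-fewer rule nor any conclusion drawn from the data. Choosing 42% with 36 patients over 40% with 46 is a fair trade-off for a single-arm phase II study.

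These figures assume that exactly 36 patients are evaluable for the primary endpoint, as 12.1 and 12.3 state, and that the one-sided exact test is applied as written. With fewer evaluable patients the power would differ at both rates.

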## 12.2 Demographics and Baseline Characteristics

Descriptive statistics (as appropriate: n, percent, mean, median, min and max) will be used to summarize demographic and baseline characteristics.

## 12.3 Efficacy Analysis

Objective tumor response will be tabulated overall (and by dose level if appropriate). Only participants who have completed at least 2 cycles will be evaluable for response.

### *Primary Analysis:*

The Phase I portion of the study begins by enrolling 3 patients at Dose Level 1 (see **Table 2**). Standard 3+3 rules will be followed until the maximum tolerated (or administered) dose is found. The recommended Phase 2 dose will be considered tolerable if DLT(s) are observed in at most 1 of 6 patients completing at least 2 treatment cycles at that dose level. Available toxicity information about these drugs suggests that Dose Level 2 will be the recommended Phase 2 dose, and that 9 patients will be required for the Phase 1. The 6 Phase 1 patients treated at the recommended Phase 2 dose will be included in Stage 1 of the Phase 2 study.

The Phase 2 study's primary endpoint is the PFS rate, defined as the proportion of patients who survive without disease progression (per RECIST criteria) for least 18-weeks after the start of treatment. Patients who progress or die (due to disease or any cause) prior to 18-weeks will be counted as failures.

The following hypothesis about the true 18-week PFS rate ( $p$ ) will be evaluated using a one-sided exact binomial test:

$$H_0: p = 0.25 \text{ versus } H_1: p > 0.25.$$

If  $T = 12$  or fewer PFS responses are observed among the total  $n_1 + n_2 = 36$  evaluable patients, the therapy will be deemed ineffective; otherwise, it will be concluded that the therapy is promising. The analysis will be conducted in SAS v9.4 (Cary, NC) at a nominal significance level of  $\alpha=0.10$ .

*Secondary Analysis:* In Phase II the secondary outcomes include: overall (OS) and progression free (PFS) survival, and toxicities. A survival event is defined as a patient who experiences death from cancer or any cause, while a patient is considered censored if they are alive at the end of the

study or at last visit before being lost to follow-up. The survival time is defined as the time from treatment until the survival event or censoring. The PFS will be as defined in the primary analysis. The OS and PFS are considered bivariate time-to-event data, and will be summarized using standard Kaplan-Meier methods. Estimates of median OS and PFS will be obtained with corresponding 90% confidence intervals. If the true median OS or PFS with the new treatment is 10.2 or 3.0 months, a 60% improvement over historical controls (6.4 and 1.9 month median OS and PFS, respectively); then Phase II estimates of the median will have interval widths of approximately 9.9 or 3.2 months for OS and PFS, respectively. The observed toxicities and adverse events will be reported as frequencies and relative frequencies, with toxicity rates estimated by 90% Wilson confidence intervals. If the true overall toxicity or adverse event rate is 0.10 to 0.50; then Phase II estimates of these rates will have interval widths of approximately 0.17 to 0.26.

## **12.4 Safety Analysis**

DLTs are the primary endpoint of this study and are used in the estimation of the MTD and the accompanying of the dose escalation decisions. However, no formal analyses of DLTs are planned. Participants who do not have a DLT and who do not complete a full cycle of treatment will be considered non-evaluable for DLT.

### **12.4.1 Adverse Event**

The frequency of toxicities will be tabulated by grade across all dose levels and cycles. The frequency of toxicities will also be tabulated for the dose estimated to be the MTD. All participants who receive any study treatment will be considered evaluable for toxicity.

## **12.5 Interim Analysis and Criteria for Early Termination of the Study**

The first portion of this study is a Phase 1 study and as such will be monitored and discussed by RPCI's Phase 1 Committee, which meets on a regular basis per the RPCI Data Safety Monitoring Plan. Drug safety will be monitored and evaluated continuously throughout the study including 30 day safety follow-up period by obtaining, reviewing and analyzing data on AEs, changes in laboratory values, vital signs, electrocardiograms (ECGs), and physical examination findings. Potential early termination decisions are an inherent part of the Phase 1 study monitoring.

There is no formal interim analysis planned or early termination criteria for the Phase II study. However, toxicity and safety outcomes will be regularly reviewed.

## **12.6 Pharmacokinetic or Pharmacokinetic/Pharmacodynamic Analysis**

### **PK/PD Modeling:**

A mechanistic PK/PD model will be developed to characterize the time course of nintedanib concentrations in relation to target decreases in sVEGFR-2 and FGF23. Subsequently, diagnostic plots will be created to ascertain whether a trend exists among sVEGFR-2 levels, FGF23, and progression free survival (PFS). If trends exist, these endpoints will also be included in the PK/PD model. A variety of compartmental population PK models will be evaluated using a nonlinear mixed effects modeling approach. The PK models explored will be described by the

estimation of mean structural parameters (e.g., plasma volumes of distribution and clearances), the magnitude of inter-individual variability (IIV) in these parameters, and residual variability (RV). The model for IIV will be assumed that the variance is proportional with respect to the typical value of the PK parameter. This analysis will include evaluation of the influence of a limited number of patient covariates, such as demographics along with other cofactors, on the variability in select PK/PD parameters. Based on our sparse sampling approach, prior information on PK parameters and variances can be used with a Bayesian estimation method. For comparisons of hierarchical models, the change in the minimum value of the objective function (MVOF), a statistic that is proportional to minus twice the log likelihood of the data, will be examined. A change in the MVOF of greater than 7.88 between two hierarchical models represents a statistical difference at a p-level of 0.005 for the addition of one parameter ( $df = 1$ ). The goodness-of-fit analyses will be additionally assessed by: (1) scatterplots of measured concentrations and weighted residuals versus population predicted concentrations, and weighted residuals versus time since first and last dose; (2) scatterplots of measured concentrations, individual weighted residuals, and absolute individual weighted residuals versus individual predicted concentrations; (3) the precisions of the parameter estimates as measured by the percent standard error of the mean ( $\%SEM = \text{standard error/parameter estimate} * 100\%$ ); (4) changes in the estimates of IIV and RV; and (5) histograms, boxplots, and plots of quantiles of individual and population weighted residuals versus quantiles of the normal distribution (QQ plots).

## **13 ETHICAL AND REGULATORY STANDARDS**

### **13.1 Ethical Principles**

This study will not be initiated until the protocol and informed consent document(s) have been reviewed and approved by a properly constituted Institutional Review Board (IRB) or Independent Ethics Committee (IEC) at each investigational site. Each participant (or legal guardian) shall read, understand, and sign an instrument of informed consent prior to performance of any study-specific procedure. It is the responsibility of the investigator to ensure that the participant is made aware of the investigational nature of the treatment and that informed consent is given.

The Investigator is responsible for the retention of the participant log and participant records; although personal information may be reviewed by authorized persons, that information will be treated as strictly confidential and will not be made publicly available. The investigator is also responsible for obtaining participant authorization to access medical records and other applicable study specific information according to Health Insurance Portability and Accountability Act regulations (where applicable).

This study will be conducted in compliance with all applicable laws and regulations of the state and/or country and institution where the participant is treated, in accordance with the Declaration of Helsinki, Good Clinical Practice, and according to the guidelines in this protocol, including attached appendices.

### **13.2 Informed Consent**

The Investigator (or IRB specified designee) is responsible for obtaining written consent from each participant or the participant's legally authorized representative in accordance with ICH-GCP guidelines using the approved informed consent form, before any study specific procedures (including screening procedures) are performed. The informed consent form acknowledges all information that must be given to the participant according to ICH-GCP, including the purpose and nature of the study, the expected efficacy and possible side effects of the treatment(s), and specifying that refusal to participate will not influence further options for therapy. Any additional information that is applicable to the study must also be included. Additional national or institutionally mandated requirements for informed consent must also be adhered to. The participant should also be made aware that by signing the consent form, processing of sensitive clinical trial data and transfer to other countries for further processing is allowed.

The Investigator shall provide a copy of the signed consent form to the participant and the signed original shall be maintained in the Investigator File. A copy of the signed consent form must be filed in the participant file. At any stage, the participant may withdraw from the study and such a decision will not affect any further treatment options.

